#### 2 General Considerations

#### 2.1 Telemedicine Virtual Visits

Telemedicine virtual visits will be completed using the existing trial equipment and systems for virtual visits.

#### 2.2 Reconsent

If there is an immediate need to reconsent subjects during the period of COVID-19 restrictions, a paper reconsent process will be followed and sites are encouraged to contact the clinical research organization (CRO) and sponsor with questions.

#### 2.3 Protocol Deviations

Protocol deviations that occur as a direct result of the COVID-19 pandemic must be recorded in eSource separately from other protocol deviations as soon as they are identified and will be recorded as "Major" in eSource for data capture purposes. Examples of the types of COVID-19 related deviations to be reported may include: missed visits, missed assessments, assessments performed remotely (completed outside of protocol procedure), missed investigational medicinal product (IMP) dose, IMP dispensed/returned via courier, IMP not returned to site/site unable to verify medication compliance, out of window visits, changes in rater, and prohibited concomitant medication. A "direct result" is defined as being due to actual illness, or as a result of quarantine, social distancing, or site closures. All other deviations will follow the normal deviation process described in the protocol and should not be entered proactively by sites.

## 2.4 Guidance to Record Adverse Events and Discontinuations Due to COVID-19

If a subject tests positive OR is presumed positive with COVID-19, the subject may continue in the trial with virtual visits only at the discretion of the investigator as long as they remain asymptomatic for COVID-19, but an adverse event (AE) of "Coronavirus Infection" OR "Coronavirus Positive Test Result" must be recorded on the AE page of the electronic case report form (eCRF). All subjects who have mild symptoms of COVID-19 must be reviewed with the medical monitor and approval must be received for the subject to continue in the trial. A positive test result or a presumed positive subject is not automatically a serious adverse event (SAE), unless an SAE criterion is met (eg, hospitalization). If the event meets the criterion for an SAE, then the subject will be discontinued from the trial.

If a subject discontinues due to COVID-19 either because the subject tests positive OR is presumed positive with COVID-19, then the primary reason for discontinuation should be reported as "Adverse Event" and indicate the AE number in the "Specify the reason for discontinuation" space that corresponds with the AE of "Coronavirus Infection" OR "Coronavirus Positive Test Result." Be sure to remember to enter an AE in the AE form for the "Coronavirus Infection" OR "Coronavirus Positive Test Result."

If a subject discontinues due to COVID-19 other than the subject testing positive OR being presumed positive with COVID-19, then the primary reason for discontinuation should be reported as "Other." Be sure to specify the reason as "COVID-19" followed by the reason ensuring that the prefix of the description includes "COVID-19." Do note that the reason "Other" should be selected even if the subject decides to withdraw consent or if the investigator decides to withdraw the subject due to COVID-19 concerns.

In case of a caregiver that is COVID-19 positive and another caregiver is available to continue the trial, the situation should be discussed with the medical monitor to determine continuation in the trial on a case-by-case basis. If there is no other caregiver, the subject needs to be early terminated from the trial.

### 2.5 Statistical Analyses

Any impact of COVID-19 on the planned statistical analyses for the trial will be described in the final statistical analysis plan.

#### 2.6 Clinical Outcomes

The administration of scales at virtual visits should be performed as described in the protocol, CCI

To decrease variability, sites should attempt to standardize the method of administration for a scale for an individual subject and across all subjects in the trial. Assessments should be administered by the same qualified/trained rater who rated the subject previously; if this is not possible due to staff availability and/or technological limitations, discuss relevant information with previous raters to obtain clinical context (note that per protocol raters must be trained/qualified to conduct assessments in all cases). Raters should conduct all assessments for that visit during the same remote session, where possible.

Please refer to Study Operations Manual for modification of administration methods for virtual visits.

## 3 Trial Population

#### 3.1 Inclusion Criteria

There are no changes to the inclusion criteria due to COVID-19 for purposes of this addendum. For delayed rollover subjects, inclusion criteria can be found in Section 3.4.2 of the protocol.

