#### 3.4.2 Inclusion Criteria

Subjects are required to meet the inclusion criteria presented in Table 3.4.2-1.

Tabl	Table 3.4.2-1 Inclusion Criteria							
1.	Subjects who, in the opinion of the investigator, could potentially benefit from administration of oral brexpiprazole for the treatment of irritability associated with ASD and who completed Trial 331-201-00148.							
2.	Male and female subjects 5 to 17 years of age, inclusive, at the time of informed consent/assent. Subjects who turned 18 years old during Trial 331-201-00148 are permitted in this trial.							
3.	Written informed consent/assent obtained from a legally acceptable representative (eg, guardian) or subject prior to the initiation of any protocol-required procedures. In addition, the subject must provide informed assent at screening and must be able to understand that he or she can withdraw from the trial at any time. All informed consent/assent procedures must be in accordance with the trial site's IRB/IEC and local regulatory requirements.							
4.	Ability, in the opinion of the principal investigator, of the subject or the subject's legally acceptable representative (eg, guardian) or caregiver(s) to understand the nature of the trial and follow protocol requirements, including the prescribed dosage regimens, tablet ingestion, and discontinuation of prohibited concomitant medications, to read and understand the written word in order to complete subject-reported outcomes measures, and to be reliably rated on assessment scales.							

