### 3.4.3 Exclusion Criteria

Subjects will be excluded if they meet any of the exclusion criteria in Table 3.4.3-1.

Tabl	e 3.4.3-1 Exclusion Criteria
1.	Subjects with a substantial protocol violation during the course of their participation in the double-blind phase 3 Trial 331-201-00148. Lesser violations such as occasional visits outside of the acceptable window or a missing blood draw will not exclude a subject from participation in Trial 331-201-00191; however, continual lack of compliance with the visit schedule, trial assessments, or treatment regimen in the prior double-blind trial would be considered a substantial violation that would result in exclusion from Trial 331-201-00191. The medical monitor should be contacted if the investigator is unsure of a subject's eligibility.
2.	Sexually active males or FOCBP who do not agree to practice 2 different methods of birth control or remain abstinent during the trial and for 30 days after the last dose of IMP. If employing birth control, 2 of the following precautions must be used: vaginal diaphragm, intrauterine device, birth control pill, birth control implant, birth control depot injection, condom with spermicide, or sponge with spermicide.

Tabl	e 3.4.3-1 Exclusion Criteria
3.	Females who are breast-feeding and/or who have a positive pregnancy test result prior to receiving IMP.
4.	Subjects who, in the opinion of the investigator, medical monitor, or sponsor, should not participate in the trial.
5.	Subjects who are siblings, or are unrelated and live in the same household, cannot simultaneously participate in the trial.

FOCBP = females of child-bearing potential

Subjects must agree to restrictions to medications and lifestyle as described in Section 4.

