## 1 Trial 331-201-00191 COVID-19 Protocol Summary

#### 1.1 Trial Design Schematic

[figure not shown]

Figure 1.1-1 COVID-19 Impact Trial Design Schematic - Subjects Who Rollover Directly From Trial 331-201-00148

Note: In order to be eligible for this trial, the baseline visit must be in office per the protocol. Eligible subjects are those subjects who complete Trial 331-201-00148. Subjects who were not able to rollover directly into this trial (Trial 331-201-00191) or are terminated early from Trial 331-201-00148 due to the COVID-19 pandemic will have an opportunity to enter this trial upon completion of in office screening and baseline visits as detailed in Figure 1.1-2.

[figure not shown]

Figure 1.1-2 Trial Design Schematic - Delayed Rollover Subjects From Trial 331-201-00148

Note: In order to eligible for this trial, the screening and baseline visits must be in office.

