#### 3.2 Exclusion Criteria

There are no changes to exclusion criteria for subjects who rollover directly from Trial 331-201-00148.

Delayed rollover subjects (ie, those who were unable to directly rollover from Trial 331-201-00148 due to the COVID 19 pandemic or who were terminated early due to the COVID-19 pandemic) will be excluded if they meet any of the exclusion criteria presented in Table 3.2-1.

Tab	Die 3.2-1 Exclusion Criteria for Delayed Rollover Subjects From Trial 331-201-00148
1.	Sexually active males or FOCBP who do not agree to practice 2 different methods of birth control or remain abstinent during the trial and for 30 days after the last dose of IMP. If employing birth control, 2 of the following precautions must be used: vaginal diaphragm, intrauterine device, birth control pill, birth control implant, birth control depot injection, condom with spermicide, or sponge with spermicide.
2.	Females who are breast-feeding and/or who have a positive pregnancy test result prior to receiving IMP.
3.	Subjects who have a significant risk of committing violent acts, serious self-harm, or suicide based on history or routine psychiatric status examination, or those who are homicidal or considered to be a high risk to others, or subjects with an answer of "yes" on C-SSRS Suicidal Ideation Item 4 (Active Suicidal Ideation with Some Intent to Act, Without Specific Plan) at entry or within the past three months, OR Subjects with a response of "yes" on the C-SSRS Suicidal Ideation Item 5 (Active Suicidal Ideation with Specific Plan and Intent) at entry or within the past three months, OR Subjects with a response of "yes" on any of the 5 C-SSRS Suicidal Behavior Items(actual attempt, interrupted attempt, aborted attempt, preparatory acts, or behavior) at entry or within the past year.
4.	Non-pharmacological therapy (eg, psychotherapy, behavior modification) is not stable for 30 days prior to screening and is not likely to be consistent throughout the trial.
5.	
 
Subjects with Type I or Type II diabetes are excluded if all of the following criteria are not met:
 
HbA1c ≤ 6.5%,
 
Screening fasting glucose is ≥ 70 mg/dL and ≤ 100 mg/dL or nonfasting glucose is ≥ 70 mg/dL and ≤ 139 mg/dL. If the nonfasting glucose is ≥ 139 mg/dL, subjects must be retested in the fasting state. At retest, fasting glucose must be ≤ 100 mg/dL
 

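### The COVID-19 addendum admits subjects terminated early from the parent trial, but unchanged inclusion criterion 1 and the SAP Enrolled Sample, read literally, shut them out

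*Protocol*

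**What the plan says.** **Entry route.** The note to Figure 1.1-1 in Addendum 1.1 gives the general rule: "Eligible subjects are those subjects who complete Trial 331-201-00148". It then adds that subjects who could not roll over directly, or who "are terminated early from Trial 331-201-00148 due to the COVID-19 pandemic will have an opportunity to enter this trial", once in-office screening and baseline visits are done. Note a to Table 1.2-1 repeats this. Addendum 3.2 counts among delayed rollovers those "who were terminated early due to the COVID-19 pandemic".

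**Inclusion criteria.** Addendum 3.1 says: "There are no changes to the inclusion criteria due to COVID-19 for purposes of this addendum". It continues: "For delayed rollover subjects, inclusion criteria can be found in Section 3.4.2 of the protocol". Criterion 1 in that section covers subjects who could benefit from treatment of irritability "associated with ASD and who completed Trial 331-201-00148". Protocol 3.3.1 requires all subjects to meet the enrollment criteria before entry.

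**Exclusion criteria.** Addendum 3.2 leaves the exclusions unchanged for direct rollovers and gives delayed rollovers their own eleven-item list, Table 3.2-1. The main list, protocol Table 3.4.3-1, has five items. Exclusion 1 is "Subjects with a substantial protocol violation during the course of their participation in the double-blind phase 3 Trial 331-201-00148" and exclusion 5 is "Subjects who are siblings, or are unrelated and live in the same household, cannot simultaneously participate in the trial".

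**Analysis sets.** SAP 5.1 confines the Enrolled Sample to subjects who finished the parent trial's double-blind period, gave consent or assent, and met all eligibility criteria. Its Safety Sample is the dosed part of the Enrolled Sample, and its Efficacy Sample is drawn from the Safety Sample. Protocol 7.2 defines the Safety Sample as everyone who takes at least one dose, with no completion condition.

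**The concern.** The addendum opens a door in one section and leaves it locked in another. A site working through the inclusion checklist cannot tick criterion 1 for a subject whose parent trial was cut short, yet the addendum provides a schedule of assessments and an exclusion table for that subject. The site must either refuse a subject the addendum means to admit, or enrol the subject against criterion 1. Protocol 3.13 names enrolment in violation of eligibility criteria as an example of a significant deviation.

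The same conflict reaches the analysis. Safety is the primary objective, and the SAP runs every safety summary on a sample that carries the completion condition. A subject who was dosed and followed could be missing from the primary safety denominator under the SAP and present in it under the protocol.

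The exclusion list raises a secondary question. Addendum 3.2 does not say how Table 3.2-1 relates to Table 3.4.3-1, so it is unclear whether parent-trial compliance and the same-household rule still apply to delayed rollovers.

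**Working it through.** The plan states no figure to reproduce. The check sets the passages side by side.

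**Step 1: entry.** Take a subject terminated early from the parent trial because of COVID-19.

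| Source | Result for this subject |
|---|---|
| Addendum 1.1, note to Figure 1.1-1 | may enter |
| Addendum Table 1.2-1, note a | may enter |
| Addendum 3.2, definition of delayed rollover | counted as a delayed rollover |
| Addendum 3.1 | inclusion criteria unchanged; go to protocol 3.4.2 |
| Protocol 3.4.2, criterion 1 | fails: parent trial not completed |
| Protocol 3.3.1 | all enrollment criteria must be met |

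Three places admit the subject. The last three, taken together, refuse the subject. No exception to criterion 1 is written anywhere.

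**Step 2: analysis sets, assuming the subject is enrolled and dosed.**

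| Set | Condition | Included? |
|---|---|---|
| SAP Enrolled | parent double-blind period completed, and all criteria met | no, on both counts |
| SAP Safety | Enrolled and dosed | no |
| SAP Efficacy | SAP Safety, with baseline and post-baseline ABC-I | no |
| Protocol Safety | at least one dose | yes |

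SAP 7.1 has a baseline rule for subjects with separate screening visits after the parent trial, so delayed rollovers are expected in the analysis. A delayed rollover who did complete the parent trial passes both tables. The conflict is confined to those terminated early.

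**Step 3: exclusions, Table 3.4.3-1 mapped to Table 3.2-1.**

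| Main exclusion | Delayed-rollover item |
|---|---|
| 1, substantial violation | none |
| 2, contraception | 1 |
| 3, pregnancy or breast-feeding | 2 |
| 4, discretionary (investigator, medical monitor or sponsor) | 11, investigator only |
| 5, siblings or same household | none |

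Two of five have no counterpart. Three are repeated, and the no-change statement is limited to direct rollovers; both facts favour reading Table 3.2-1 as a replacement. Protocol 3.3.1 and 3.4.3 speak of subjects without distinction, which allows reading it as a supplement. Protocol section 3 still describes entrants as judged compliant with the parent protocol.

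**Step 4: size.** SAP section 4 caps the sample at the 119 subjects randomized in the parent trial. One affected subject is therefore at least 1/119 = 0.84% of the sample. The number of affected subjects is not given.

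**The case against.** The strongest reply is that the intent is plain. The permission is specific, is given more than once, and comes with its own schedule and exclusion table, so a sensible site would raise a query or record a deviation rather than turn the subject away. The note that eligible subjects are completers reads naturally as a general rule followed by its exception. Both points stand. They show what was meant, but they do not supply the missing words in criterion 1, and Addendum 3.1 expressly sends delayed rollovers there.

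On the analysis sets, SAP 5.1 also says that a subject leaves the Safety Sample only on evidence of never having taken the drug. That suggests all dosed subjects were meant to count. The sentence still operates within a set defined as Enrolled subjects, so the definition needs repair.

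A reader might go further in four ways that the documents do not support:

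- **Two exclusions have been dropped, leaving an open door.** The addendum never says that Table 3.2-1 replaces the main list. Even if it does, item 11 allows exclusion on the investigator's opinion, inclusion criterion 4 requires ability to follow the protocol and dosage regimen, and section 3 expects compliant entrants. These safeguards are discretionary, but they exist.
- **A subject refused at direct rollover could come in late.** Protocol 3.7.1.1 and 3.9 bar rescreening of rollover subjects who did not qualify.
- **Two subjects' drug supplies could end up in one home.** Exclusion 5 is worded as a bar on simultaneous participation in the trial as a whole, and the documents do not give its purpose.
- **Subjects who turned 18 in the gap between trials are wrongly shut out.** Criterion 2 sets an age range with one narrow exception. No passage says those subjects were to be admitted, so nothing conflicts.

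**Conclusion.** The inconsistency is real and needs no inference. Addendum 3.1 with protocol criterion 1 contradicts Addendum 1.1, Table 1.2-1 note a and Addendum 3.2 for subjects terminated early from the parent trial because of COVID-19. Followed literally, the text refuses them or makes them eligibility violations. If they are dosed, it leaves them out of all three SAP analysis sets while the protocol Safety Sample keeps them.

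The practical size is unknown. It could be zero: SAP 3.1 and section 4 describe participants only as parent-trial completers. The 0.8% is a floor on the weight of one such subject and does not show that any exist. All analyses are descriptive, so no test or power statement is affected; what is at stake is who counts in the primary safety denominator.

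The exclusion question is a lesser one. The documents support saying that the relation between the two tables is unstated, with replacement the more natural reading. They do not support treating the loss of exclusions 1 and 5 as established.

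**What to change.** 1. In Addendum 3.1, replace the no-change statement for delayed rollovers with the exception to criterion 1 that the addendum already grants to subjects terminated early from Trial 331-201-00148 because of COVID-19. This reconciles it, and protocol 3.4.2, with Addendum 1.1, Table 1.2-1 note a and Addendum 3.2.
2. In SAP 5.1, align the Enrolled and Safety Sample definitions with that exception and with protocol 7.2, so that every dosed delayed rollover is in the Safety Sample. The Efficacy Sample then follows from its own ABC-I conditions.
3. In Addendum 3.2, add a sentence saying whether Table 3.2-1 replaces or supplements Table 3.4.3-1, and so whether exclusions 1 and 5 apply to delayed rollovers. The sponsor decides which.

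The cost is wording in the addendum and the SAP. No visit, assessment or analysis is added.

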#### 3.2 Exclusion Criteria

There are no changes to exclusion criteria for subjects who rollover directly from Trial 331-201-00148.

Delayed rollover subjects (ie, those who were unable to directly rollover from Trial 331-201-00148 due to the COVID 19 pandemic or who were terminated early due to the COVID-19 pandemic) will be excluded if they meet any of the exclusion criteria presented in Table 3.2-1.

Tab	Die 3.2-1 Exclusion Criteria for Delayed Rollover Subjects From Trial 331-201-00148
1.	Sexually active males or FOCBP who do not agree to practice 2 different methods of birth control or remain abstinent during the trial and for 30 days after the last dose of IMP. If employing birth control, 2 of the following precautions must be used: vaginal diaphragm, intrauterine device, birth control pill, birth control implant, birth control depot injection, condom with spermicide, or sponge with spermicide.
2.	Females who are breast-feeding and/or who have a positive pregnancy test result prior to receiving IMP.
3.	Subjects who have a significant risk of committing violent acts, serious self-harm, or suicide based on history or routine psychiatric status examination, or those who are homicidal or considered to be a high risk to others, or subjects with an answer of "yes" on C-SSRS Suicidal Ideation Item 4 (Active Suicidal Ideation with Some Intent to Act, Without Specific Plan) at entry or within the past three months, OR Subjects with a response of "yes" on the C-SSRS Suicidal Ideation Item 5 (Active Suicidal Ideation with Specific Plan and Intent) at entry or within the past three months, OR Subjects with a response of "yes" on any of the 5 C-SSRS Suicidal Behavior Items(actual attempt, interrupted attempt, aborted attempt, preparatory acts, or behavior) at entry or within the past year.
4.	Non-pharmacological therapy (eg, psychotherapy, behavior modification) is not stable for 30 days prior to screening and is not likely to be consistent throughout the trial.
5.	
 
Subjects with Type I or Type II diabetes are excluded if all of the following criteria are not met:
 
HbA1c ≤ 6.5%,
 
Screening fasting glucose is ≥ 70 mg/dL and ≤ 100 mg/dL or nonfasting glucose is ≥ 70 mg/dL and ≤ 139 mg/dL. If the nonfasting glucose is ≥ 139 mg/dL, subjects must be retested in the fasting state. At retest, fasting glucose must be ≤ 100 mg/dL
 

	• Subject has been maintained on a stable regimen of non-insulin medication(s) for at least 28 days prior to screening or diabetes has been well-controlled by diet for at least 28 days prior to screening,
	
 
Subject has not had any hospitalizations within the 12 months prior to screening due to diabetes or complications related to diabetes, AND
 

	Subject's diabetes is not newly diagnosed during screening for the trial.

Tabl	Exclusion Criteria for Delayed Rollover Subjects From Trial 331-201-00148
6.	Subjects with uncontrolled hypertension or symptomatic hypotension, or orthostatic hypotension which is defined as a decrease of $\geq 15$ mmHg in SBP or a decrease of $\geq 15$ mmHg in DBP after at least 3 minutes standing compared to the previous supine blood pressure, OR development of symptoms.
7.	Subjects ≥ 13 years of age that engage in social activities with peers without adult supervision who test positive for drugs of abuse or with a positive blood alcohol test at screening are excluded. A positive test for amphetamines, barbiturates, opiates, benzodiazepines may not result in exclusion of the subjects if the investigator determines that the positive test is a result of prescription medicine(s). When a subject tests positive for cannabinoids (tetrahydrocannabinol) at screening, the investigator is required to evaluate the subject's ability to abstain from using this substance during the trial and to discuss his/her evaluation with the Medical Monitor prior to randomization.
8.	
 
The following laboratory test and ECG results are exclusionary: 
 
Platelets ≤ 130 × 10³/uL for ≤ 12 years of age, ≤ 140 × 10³/uL for ≥ 13 years of age
 
Hemoglobin ≤ 11.2 g/dL for ≤ 12 years of age, ≤ 11.6 g/dL for ≥ 13 years of age
 
Neutrophils, absolute ≤ 1.00 × 10³/uL for ≤ 12 years of age, ≤ 1.35 × 10³/uL for ≥ 13 years of age
 
AST ≥ 2 × upper limit of normal
 
ALT ≥ 2 × upper limit of normal
 
Creatinine ≥ 0.7 mg/dL for ≤ 12 years of age, ≥ 1.1 mg/dL for ≥ 13 years of age
 
HbA1c ≥ 6.5%
 
CPK ≥ 2 × upper limit of normal
 
QTcF ≥ 450 msec for males and ≥ 470 msec for females using the QTcF correction
 
 
 

9.	The subject weighs < 15 kg.
10. 11.	Subjects who would be likely to require prohibited concomitant therapy during the trial.  Any subject who, in the opinion of the investigator, should not participate in the trial.

ALT = alanine aminotransferase; AST = aspartate aminotransferase; CPK = creatine phosphokinase; C-SSRS = Columbia-Suicide Severity Rating Scale; FOCBP = females of childbearing potential; HbA1C = Glycosylated hemoglobin; QTcB = QT interval corrected for heart rate by Bazett's formula; QTcF = QT interval corrected for heart rate by Fridericia's formula.

